7.2 General Study Procedures

An overview of study assessments/procedures is provided below. A description for each phase of the study is provided in [Section 7.3](#) through [Section 7.6](#). Refer to the eCRF completion guidelines for data collection requirements and documentation of study assessments/procedures.

7.2.1 Informed Consent

All subjects or their legally acceptable representative (ie, legal guardian) must sign and date the most current IRB/EC approved ICF. Confirmation that the ICF has been signed should occur before any study specific procedures are performed.

All subjects who are enrolled and receive protocol-specified therapy or specified treatment should be re-consented with any updated versions of IRB/EC approved informed consents during study participation as applicable and per institutional guidelines.

7.2.2 Demographics

Demographic data that will be collected include sex, age, race, and ethnicity to study their possible association with subject safety and treatment effectiveness. Additionally demographic data will be used to study the impact on PK of blinatumomab.

7.2.3 Medical History

The Investigator or designee will collect relevant medical history before the start of adverse event reporting.

In addition to the medical history noted above, all history related to the subjects diagnosis of ALL (eg, risk stratification, immunophenotype, information on prior anti-tumor therapies and HSCT data) must date back to the original diagnosis.

7.2.4 ECOG Performance Status

The subject's PS will be assessed using the ECOG performance scale (see [Appendix E](#)) at intervals identified in the Schedule of Assessments ([Table 9](#)).

7.2.5 Physical Examination

The baseline physical examination will be a complete physical examination. The physical examination at subsequent study visits will consist of an interim examination to monitor for any changes from the baseline physical examination. Abnormal findings should be documented in the appropriate eCRF.

Approved

7.2.6 Physical Measurements

Height should be measured without shoes. Weight should be measured without shoes. The baseline assessment includes height and weight. The SFU physical measurements will include weight only.

7.2.7 Vital Signs

Systolic/diastolic blood pressure, heart rate, respiratory rate, and temperature are measured as per Schedule of Assessments (Table 9). Subject must be in a supine position in a rested and calm state for at least 5 minutes before blood pressure assessments are conducted. If the subject is unable to be in the supine position, the subject should be in most recumbent position as possible. The position selected for a subject should be the same that is used throughout the study and documented on the vital sign eCRF.

Record all measurements on the vital signs eCRF.

The temperature location selected for a subject should be the same that is used throughout the study and documented on the eCRF.

7.2.8 Neurological Examination

A neurological examination will be performed as outlined in the Schedule of Assessments (Table 9). Subjects will be specifically queried for neurological symptoms observed in the interval since the last extended neurological examination. Abnormalities of the following should be recorded: level of consciousness, orientation, vision, cranial nerves and brain stem functions, pyramidal and extra pyramidal motor system, reflexes, muscle tone and trophic findings, coordination, sensory system, and neuropsychological findings (eg, speech, cognition and emotion). If neurologic abnormalities are present at screening, then they will be considered as medical history. Any new findings on neurological examination during the study will be considered adverse events and graded per CTCAE Version 4.03.

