9. SAFETY DATA COLLECTION, RECORDING, AND REPORTING

9.1 Definition of Safety Events

9.1.1 Disease Related Events

Disease Related Events are events (serious or non-serious) anticipated to occur in the study population due to the underlying disease. Please refer to [Appendix D](#) for disease related events by system organ class. Such events do not meet the definition of an Adverse Event unless assessed to be more severe than expected for the subject's condition. All serious disease-related events will be recorded and reported to the sponsor or designee within 24 hours.

Disease-related events that would qualify as an adverse event or serious adverse event:

- An event based on the underlying disease that is worse than expected as assessed by the investigator for the subject's condition or if the investigator believes there is a causal relationship between the investigational product(s)/study treatment/protocol-required therapies and disease worsening, this must be reported as an adverse event or serious adverse event.

Disease Related Events and/or Disease Related Outcomes that do not qualify as Serious Adverse Events:

- An event which is part of the normal course of disease under study (eg, disease progression in oncology or hospitalization due to disease progression) is to be reported as a Disease Related Event.
- Death due to the disease under study is to be recorded on the Event eCRF.

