9.1.3 Serious Adverse Events

A serious adverse event is defined as an adverse event that meets at least 1 of the following serious criteria (unless it meets the definition of a Disease Related Event as defined in [Section 9.1.1](#)):

- fatal
- life threatening (places the subject at immediate risk of death)
- requires in-patient hospitalization or prolongation of existing hospitalization
- results in persistent or significant disability/incapacity
- congenital anomaly/birth defect
- other medically important serious event

A disease related event as listed in [Appendix D](#) is to be reported as a serious adverse event if

- the subject's pre-existing condition becomes worse than what the investigator would consider typical for a patient with the same underlying condition, or
- if the investigator believes a causal relationship exists between the investigational medicinal product(s)/protocol-required therapies and the event,
- and the event meets at least 1 of the serious criteria above.

An adverse event would meet the criterion of "requires hospitalization", if the event necessitated an admission to a health care facility (eg, overnight stay), and/or treatment that would not have been appropriate in the physician's office or outpatient setting. Complications that occur during hospitalization are an adverse event. If a complication prolongs a hospitalization or fulfills any other serious criteria, the event is serious. When in doubt as to whether "hospitalization" occurred or was necessary, the adverse event is to be considered serious. Hospitalization for elective treatment of a pre-existing condition that did not worsen from baseline is not considered an adverse event.

The term disability means a substantial disruption of a person's ability to conduct normal life functions. The definition is not intended to include experiences of relatively minor medical significance such as uncomplicated headache, nausea, vomiting, diarrhea, influenza, and accidental trauma (eg, sprained ankle) which may interfere with or prevent everyday life functions but do not constitute a substantial disruption.

If an investigator considers an event to be clinically important, but it does not meet any of the serious criteria, the event could be classified as a serious adverse event under the criterion of "other medically important serious event". Examples of such events could include invasive or malignant cancers, intensive treatment in the emergency room or at

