9.2 Safety Event Reporting Procedures

9.2.1 Reporting Procedures for Disease Related Events

The investigator is responsible for ensuring that all Disease Related Events observed by the investigator or reported by the subject that occur after the first dose of protocol-required therapies through the SFU visit are recorded using the Event eCRF as a disease-related event.

All serious disease-related events will be recorded and reported to the sponsor or designee within 24 hours. The investigator will submit any updated serious disease-related event data to the sponsor within 24 hours of it being available.

Disease-related events assessed by the investigator to be more severe than expected and/or related to the investigational medicinal product(s)/study treatment/protocol-required therapies, and determined to be serious, must be recorded on the Event CRF as serious adverse events, and reported per [Section 9.2.2.2](#).

Additionally, the investigator is required to report a fatal Disease Related Event on the Event eCRF.

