Appendix D. Expected Disease-related Adverse Events by System Organ Class (SOC)

System Organ Class	Disease-Related Adverse Events
Blood and lymphatic system disorders	Febrile neutropenia, anemia, neutropenia, thrombocytopenia, leukopenia, lymphadenopathy
Gastrointestinal disorders	Abdominal distension, abdominal pain, constipation, diarrhea, gingival pain, nausea
General disorders and administration site conditions	Fatigue, pyrexia, malaise, bone and joint pain
Infections and infestations	Infection ^{a,b}
Investigations	White blood cell count decreased, hemoglobin decreased, platelet count decreased
Metabolism and nutrition disorders	Decreased appetite, weight loss
Musculoskeletal and connective tissue disorders	Skeletal pain, muscular pain, arthralgia, neck pain
Nervous system disorders	Dizziness, headache, lethargy, meningismus, syncope
Respiratory, thoracic and mediastinal disorders	Dyspnea, epistaxis
Other	Hemorrhage ^c

^a Represents preferred terms under infections and infestations primary SOC

^b Progressive multifocal leukoencephalopathy (PML) is excluded from the list of DRE and must be reported to Amgen in an expedited manner

^c Represents hemorrhage preferred terms under multiple SOCs

Approved

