4.1 Study Endpoints

Primary Endpoint

- CR/CRh* rate within 2 cycles of treatment with blinatumomab

Secondary Endpoints

- CR rate within 2 cycles of treatment with blinatumomab
- CR/CRh*/CRi (complete remission with incomplete hematological recovery) rate within 2 cycles of treatment with blinatumomab
- Pharmacokinetic parameters
- Overall survival
- Relapse-free survival
- MRD response rate within 2 cycles of treatment with blinatumomab
- Proportion of subjects undergoing allogeneic HSCT among those who achieved CR/CRh* after treatment with blinatumomab
- 100-day mortality after allogeneic HSCT
- Time to a 10 point decrease from baseline in global health status/Quality of Life (QoL) using the EORTC QLQ-C30.

Safety Endpoints

- Overall incidence and severity of adverse events
- Incidence of anti-blinatumomab antibody formation

Exploratory Endpoints

- **Neurological adverse events**
- Quantification and characterization of peripheral blood lymphocyte subsets
- Quantification and characterization of serum cytokines and chemokines

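### Two protocol rules classify the same neurological findings differently, so the neurological adverse event count can be too low and can vary by site

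*Protocol*

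**What the plan says.** Protocol 7.2.8 sets a rule with no exception: "Any new findings on neurological examination during the study will be considered adverse events and graded per CTCAE Version 4.03". The same section extends the examination to symptoms: "Subjects will be specifically queried for neurological symptoms observed in the interval since the last extended neurological examination". Level of consciousness is one of the domains to be recorded.

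Protocol 9.1.1 sets the opposite default for disease-related events: "Such events do not meet the definition of an Adverse Event unless assessed to be more severe than expected" for the subject's condition. The nervous system row of Appendix D lists: "Dizziness, headache, lethargy, meningismus, syncope".

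There are routes back to adverse event status:

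- Section 9.1.1 reclassifies an event that is worse than expected, or "if the investigator believes there is a causal relationship between the investigational product(s)/study treatment/protocol-required therapies and disease worsening".
- Section 9.1.3 reclassifies a listed event that meets a seriousness criterion "if the investigator believes a causal relationship exists between the investigational medicinal product(s)/protocol-required therapies and the event". Section 9.2.1 says much the same, again for serious events.

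An event that stays disease-related is still "recorded using the Event eCRF as a disease-related event" (Protocol 9.2.1).

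On the analysis side, SAP 4.1 and Protocol 10.1.1.4 name "Neurological adverse events" as an exploratory endpoint. SAP 10.6.1 forms events of interest from coded adverse events. It plans incidence tables for them, makes time to onset of neurologic events optional, and summarises duration for selected events of interest. SAP 10.7.2 covers selected CNS events and gives no selection rule.

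**The concern.** A new finding of lethargy or meningismus, or a headache elicited at the neurological examination, can be an adverse event under 7.2.8 and a disease-related event under 9.1.1. Which label it gets depends on the rule the site follows and on an investigator's view of severity and cause, in an open-label single-arm trial at about 25 centres.

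The label matters because the two types are analysed differently. Neurologic events are a selected event of interest for this drug. Protocol 2.5.2 describes neurologic and psychiatric events with blinatumomab and names headache among the events that led at least 2 subjects to discontinue. SAP 10.7.2 aims to explore how CNS events relate to the drug, and Protocol 1.4 looks for predictors of them. If investigators' attribution decides beforehand which events enter the count, both aims are weakened.

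**Working it through.** The documents state no figure for this endpoint, so there is nothing to reproduce. The check is a comparison of the texts, followed by an illustration of possible size.

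**1. Do the rules overlap?** Yes, in part. Lethargy falls under level of consciousness, and meningismus can be a sign on examination. Headache, dizziness and syncope come in through the symptom query, which looks back over the interval since the last examination. Section 7.2.8 does not say outright that a reported symptom counts as an examination finding. As extracted, Table 9 shows the examination at screening, on day 1 before infusion, and at the safety follow-up visit.

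**2. Does any text rank the rules?** None was found in 7.2.8, 9.1.1, 9.1.3, 9.2.1, Appendix D or the SAP. The title of Appendix D adds to the confusion by calling its entries adverse events, which 9.1.1 says they are not by default.

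**3. Do the exceptions close the gap?** Not fully.
- Worse than expected: back to adverse event (9.1.1).
- Serious and judged related: back to adverse event (9.1.3, 9.2.1).
- Not serious and judged related: unclear, because the causal wording in 9.1.1 is tied to worsening of the disease.
- As expected and judged unrelated: stays disease-related under 9.1.1, but is an adverse event under 7.2.8 if found at the examination.

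**4. What summary does each label receive?**

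| | Adverse event | Non-fatal disease-related event |
|---|---|---|
| Incidence | Yes | Yes, overall |
| By preferred term | Yes | Not specified |
| By worst grade | Yes | Not specified |
| Onset, duration | For selected events of interest (onset optional) | Not specified |

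Protocol 10.4.5 specifies preferred terms only for fatal disease-related events. SAP 10.6.1 specifies none for disease-related events.

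**5. Illustration of size; every input is an assumption.** Let p be the share of subjects with any neurological event (30% to 70%), f the share of those whose only such events are the five listed terms (10% to 50%), and u the share of those whose events are filed as disease-related and left out of the count (0 to 100%). Then

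reported incidence = p × (1 − f × u).

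With 120 subjects:
- u = 0: no loss, whatever p and f.
- p = 50%, f = 30%, u = 50%: 0.50 × (1 − 0.15) = 42.5%, or 51 subjects instead of 60.
- p = 50%, f = 50%, u = 100%: 0.50 × 0.50 = 25%, or 30 instead of 60.
- Largest loss in the assumed range (p = 70%, f = 50%, u = 100%): 0.70 × 0.50 = 35%, or 42 instead of 84.
- Two sites with the same patients (p = 50%, f = 30%), one with u = 0 and one with u = 100%: 50% against 0.50 × 0.70 = 35%.

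The term f × u cannot be negative, so against a count of all new neurological events the error is zero or downward.

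**The case against.** A reader might infer that the five terms are simply excluded from adverse events and that the endpoint is therefore undercounted. The documents do not support that. Events judged worse than expected return to adverse event status, as do serious events judged causal. Section 7.2.8 reaches only the scheduled examinations and their symptom query. Disease-related events are not lost, since they sit on the same Event eCRF and have their own incidence summaries. SAP 10.7.2 is not stated to exclude them, and the event-of-interest search strategy is not visible in the documents. If investigators file these events as adverse events, nothing is lost.

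The background evidence is also limited. Of the five terms, Protocol 2.5.2 mentions only headache, in a discontinuation list that gives no attribution. Active CNS leukemia is excluded at entry, but Protocol 6.6 anticipates isolated CNS leukemia arising on study, so some of these symptoms may be disease-caused.

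Nor does the exclusion of progressive multifocal leukoencephalopathy from Appendix D show that neurological terms were meant to be removed. That footnote belongs to the infection row and concerns expedited reporting. The endpoint is exploratory, and no decision rule uses it.

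All of this stands, and it makes the undercount a possibility rather than a fact. It does not remove the conflict between the sections, the unclear route for non-serious related events, or the thinner reporting of disease-related events.

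**Conclusion.** The conflict is real and unresolved. Followed as written, the plan can leave non-fatal occurrences of the five terms out of the neurologic event-of-interest tables, and possibly out of the exploratory endpoint, depending on how each site classifies them.

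The size cannot be computed, because the documents give neither the incidence of these terms nor the share that would be filed as disease-related. The illustrative losses, from none to 42 of 120 subjects, rest wholly on assumed inputs and are not estimates. The upper figure also requires every such event to be filed as disease-related and then excluded from the analysis.

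The CR/CRh* endpoint, its type I error and its power do not depend on event classification and are unaffected. This is a low-cost improvement to safety reporting, not a threat to the trial's main conclusion.

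**What to change.** In SAP 10.6.1 and 10.7.2, define neurologic events by the MedDRA search applied to all Event eCRF records, adverse events and disease-related events together. Report the adverse-event-only count as a second row. This removes the dependence on classification and also works for data already collected.

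First check that disease-related records carry grade and start and stop dates. Protocol 9.2.2.1 lists these attributes for adverse events, while 9.2.1 gives no such list for disease-related events. Without them, incidence can be pooled but grade, onset and duration cannot.

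Separately, reconcile 7.2.8 with 9.1.1 and Appendix D by stating which governs the recording of neurological findings. Deleting the nervous system row is not required. It would need a protocol amendment with ethics approval (Protocol 12.1), and it would change expedited reporting, because 9.2.2.5 exempts serious disease-related events from individual expedited reports unless they meet 9.1.3.

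The cost of the SAP change is a little programming and a higher reported neurologic count that will include some symptoms caused by the leukemia. The adverse-event-only row lets readers see the difference.

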7.2.9 Lumbar Puncture to Examine Cerebrospinal Fluid

A lumbar puncture will be performed as outlined in the Schedule of Assessments (Table 9) to assess for possible leukemic involvement. Cerebrospinal fluid (CSF), including cell count, glucose, and protein, will be measured at the local laboratory as part of the examination. Additional investigations of the CSF should be performed as clinically appropriate.

If an Ommaya reservoir is in place and there is no evidence of blockage of CSF flow in the spinal canal, withdrawal of a sample through the Ommaya reservoir is permitted.

7.2.10 Intrathecal Prophylaxis

Within 14 days before the start of protocol-specified therapy AND following each treatment cycle (after BM aspiration on Day 29) a mandatory CSF prophylaxis consisting of an intrathecal regimen will be administered (eg, methotrexate 12 to 15 mg, cytosine arabinoside 40 mg, and dexamethasone 4 mg or equivalent steroid dose).

In case of anticipated safety risks caused by lumbar puncture during the treatment period of the study (eg, in case of thrombocytopenia) CSF prophylaxis may be omitted.

7.2.11 Bone Marrow Biopsy/Aspiration

Bone marrow (BM) will be used for hematological assessment and for evaluation of MRD. The following samples will be obtained for cytomorphological assessment and MRD measurement:

- Cytomorphology: BM smears (slides) at screening and at the end of each treatment cycle. In case of insufficient quality of the aspiration material at the end of each treatment cycle, a core biopsy should be performed before treatment start in the next cycle or at the SFU visit, if the subject has not progressed and no further treatment cycles are to be administered.
- A fresh BM sample will be collected and analyzed at a central lab for MRD assessment by multi-color flow cytometry at screening and at the end of the first and second treatment cycles.

If a marrow aspiration is not possible, or the aspirate does not contain any BM, a core biopsy will be done. In case of core biopsies, no central MRD assessment will be possible due to the need to preserve the biopsy with formalin before shipment.

If a subject has not relapsed by their last induction and consolidation treatment cycle, a BM biopsy or aspirate should be performed every 3 months (\pm 1 month) until relapse.

The degree of BM infiltration defined by the percentage of leukemic blasts in BM will be evaluated by local laboratories as per cytological assessment. In addition, the BM slides will be provided to the designated central laboratories for hematological assessment. If immunocytochemistry (ICC) is not possible, then immunohistochemistry (IHC) will be done instead on the back-up core biopsy to confirm cytomorphology. The following markers will be analyzed as needed: CD3, CD5, CD10, CD13, CD19, CD22, CD23, CD33, CD34, CD79A, POX, TDT.

The results of the local laboratory are applicable for inclusion into the study and for the decision if pre-treatment and/or blinatumomab treatment should be administered if the results of the central laboratory are not yet available at the time these decisions are made. For evaluation of baseline and response, the result of the central laboratory will prevail.

Known cytogenetic and molecular aberrations will be documented in the eCRF.

Results of additional tests routinely conducted by the investigators, but not required by the protocol such as immunophenotypic, cytogenetic or molecular analyses conducted during the study, will be collected and documented in the eCRF.

Note: the time window for all BM assessments as per Schedule of Assessments in [Table 9](#).

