4.1.1 Inclusion Criteria

- 101 Subjects have provided informed consent/assent prior to initiation of any study-specific activities/procedures or subject's legally acceptable representative has provided informed consent prior to any study-specific activities/procedures being initiated when the subject has any kind of condition that, in the opinion of the investigator, may compromise the ability of the subject to give written informed consent.
- 102 Subjects with Ph-negative B-precursor ALL, with any of the following:
- Primary refractory after induction therapy or who had relapsed within 12 months of first remission or
 - Relapsed within 12 months of receiving alloHSCT or
 - Relapsed or refractory after first salvage therapy or beyond
- 103 > 5% blasts in BM (by morphology)
- 104 Eastern Cooperative Oncology Group (ECOG) performance status (PS) ≤ 2
- 105 Age ≥ 18 years at the time of informed consent

Approved

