7.2.13 Definitions of Treatment Response

The treatment is defined to be efficacious, when the subject is stated to be in CR or in CRh* or CRi.

Hematological remissions are defined by the following criteria:

Complete Remission (CR):

- Less than or equal to 5% blasts in the BM
- No evidence of disease
- Full recovery of peripheral blood counts:
 - Platelets > 100,000/ μ l
 - ANC > 1,000/ μ l

Approved

Complete Remission with only Partial Hematological Recovery (CRh*):

- Less than or equal to 5% blasts in the BM
- No evidence of disease
- Partial recovery of peripheral blood counts:
 - Platelets > 50,000/ μ l and
 - ANC > 500/ μ l

Complete Remission with only incomplete blood count recovery (CRi):

- Less than or equal to 5% blasts in the BM
- No evidence of disease
- Partial recovery of peripheral blood counts:
 - Platelets >100,000/ μ l; or
 - ANC > 1000/ μ l

Subjects who will have achieved CR or CRh* or CRi within 2 cycles of treatment will receive up to 3 additional cycles of treatment for consolidation.

Blast free hypoplastic or aplastic BM:

- Less than or equal to 5% blasts in the BM
- No evidence of disease
- Insufficient recovery of peripheral counts: platelets \leq 50,000/ μ l and/or ANC \leq 500/ μ l

The onset of remission is defined by the date of the first aspiration/biopsy on which the remission was documented.

When criteria are met for both CRh* and CRi, CRh* should be reported. When criteria are met for both CRi and blast-free marrow, CRi should be reported.

Progressive Disease:

- An increase of at least 25%, or an absolute increase of at least 5,000 cells/ μ L (whichever is greater), in the number of circulating leukemia cells, development of extramedullary disease, or other laboratory or clinical evidence of progressive disease

Non-response:

- None of the above

Hematological Relapse:

- Proportion of blasts in BM > 5% or
- Blasts in peripheral blood after documented CR/CRh*

An extramedullary relapse will be assessed as hematological relapse.

The relapse will be analyzed by immuno-phenotyping whether it still fulfills the criteria for B-precursor ALL. The onset of relapse is defined by the date of the first sample on which relapse was documented.

All hematological assessments of BM will be reviewed in a central reference laboratory.

In the event of disease progression or hematological relapse within the treatment period, treatment will be terminated.

Extramedullary disease:

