10.1.2 Analysis Sets

The statistical analysis will be based on the following study populations:

- Primary Analysis Set (PAS): All enrolled subjects who received at least one infusion of blinatumomab.
- Safety Analysis Set (SAS): All enrolled subjects who received at least 1 infusion of blinatumomab. The definition is the same as primary analysis set.
- Pharmacokinetic Analysis Set (PKS): All subjects who received any infusion of blinatumomab and had at least 1 PK sample collected will be included in the PK analysis set. These subjects will be evaluated for PK unless significant protocol deviations affect the data analysis or if key dosing, dose interruption, or sampling information is missing.

The primary analysis of efficacy and safety will be performed on PAS and SAS separately.

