A CR is defined as having $\leq 5\%$ blasts in the bone marrow, no evidence of disease, and full recovery of peripheral blood counts (platelets $> 100,000/\mu\text{L}$, and absolute neutrophil count [ANC] $> 1,000/\mu\text{L}$). CR rate is defined as the proportion of subjects who achieve CR within 2 cycles of treatment with blinatumomab. Subjects without response assessment will be accounted for in the denominator when calculating the response rate.

Complete Remission with Partial Hematological Recovery (CRh*)

CRh* is defined as $\leq 5\%$ blasts in the bone marrow, no evidence of disease and partial recovery of peripheral blood counts: platelets $> 50,000/\mu\text{L}$, and ANC $> 500/\mu\text{L}$.

Complete Remission with Incomplete Hematological Recovery (CRi)

CRi is defined as $\leq 5\%$ blasts in the bone marrow, no evidence of disease and incomplete recovery of peripheral blood counts: platelets $> 100,000/\mu\text{L}$ or ANC $> 1,000/\mu\text{L}$ (but not both).

CR/CRh*

CR/CRh* is defined as having either CR, or CRh*. CR/CRh* rate is defined as the proportion of subjects who achieve CR/CRh* within 2 cycles of treatment with blinatumomab. Subjects without response assessment will be accounted for in the denominator when calculating the response rate, ie, these subjects will be counted as non-responders.

CR/CRh*/CRi

CR/CRh*/CRi is defined as having either a CR, CRh*, or CRi. CR/CRh*/CRi rate is defined as the proportion of subjects who achieve CR/CRh*/CRi within 2 cycles of treatment with blinatumomab. Subjects without response assessment will be accounted for in the denominator when calculating the response rate.

Cumulative Dose of Blinatumomab

Blinatumomab: The cumulative dose in μg is defined as the following with summation over infusions:

$$\sum \text{duration of infusion [days] for each dose received} \times \text{dose received} [\mu\text{g/day}]$$

Cumulative dose will be calculated within a cycle and across all cycles.

Death Date

For subjects who die during the study, the death date will be recorded on the end of

study CRF as the end of study date. For deaths collected after a subject has ended study (eg, through public records or as part of adverse event (AE) reporting post end of study date), the death date will be recorded on the long term follow-up CRF in the subject status date or on the AE CRF in the AE end date for a grade 5 AE.

End of Blinatumomab Therapy Date

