7.1 Primary Analysis Set (PAS)

This dataset consists of all enrolled subjects who received at least one infusion of blinatumomab. Primary analysis will be performed when all the enrolled subjects have finished at least 2 cycles of blinatumomab and the safety follow-up visit (if subjects discontinue treatment after 2 cycles), or have discontinued the treatment of blinatumomab and complete the safety follow up visit, whichever occurs first.

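### Does entry on a local marrow reading, with baseline and response read centrally, leave the primary CR/CRh* rate exposed to subjects who had 5% blasts or fewer at the start?

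*Protocol*

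**What the plan says.** Inclusion criterion 103 (Protocol Section 4.1.1) requires more than 5% marrow blasts by morphology and names no laboratory. Protocol Section 7.2.11 supplies the missing piece: "The results of the local laboratory are applicable for inclusion into the study", and for decisions on treatment, "if the results of the central laboratory are not yet available at the time these decisions are made". It then adds: "For evaluation of baseline and response, the result of the central laboratory will prevail".

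The marrow part of both CR and CRh* is "Less than or equal to 5% blasts in the BM" (Protocol Section 7.2.13), the exact complement of the entry threshold. Marrow alone is not enough: SAP Section 6 also requires, for CR, "no evidence of disease, and full recovery of peripheral blood counts", and CRh* needs partial count recovery. Neither definition refers to the subject's baseline.

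The PAS is "All enrolled subjects who received at least one infusion of blinatumomab" (Protocol Section 10.1.2; SAP Section 7.1 agrees), with no condition on central baseline blasts. Under Protocol Section 10.4.2, subjects without a response assessment count as non-responders.

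On reporting, SAP Section 10.4 summarises the baseline marrow blast count, SAP Section 10.1 gives quartiles, minimum and maximum for continuous variables, and SAP Section 7.5 has a blast subgroup cut at 50%. Nothing is cut at 5%. The only sensitivity analyses named are for relapse-free survival.

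**The concern.** The trial has one arm and compares its rate with a fixed 30%, so no control group shares any misclassification at entry. If local and central readers disagree near 5%, some treated subjects may, by the reading that governs the endpoint, start with the marrow criterion already met. If they are scored CR/CRh* more often than 30% of the time, the PAS rate overstates the rate in subjects with centrally confirmed marrow disease.

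The planned outputs would not show how far this went. A minimum baseline blast count of 5% or less would reveal that at least one such subject exists, but not how many, or how they were scored. Because entry on a local reading is expressly allowed, these subjects need not appear as eligibility deviations.

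**Working it through.** **Inputs.** Null rate 30%, alternative 45%, N = 120, one-sided 2.5%, power 90% (Protocol Section 10.2). Boundaries 42.2% at 90 subjects and 39.2% at 120 (Protocol Section 10.3.1), that is 38/90 = 42.2% and 47/120 = 39.2%. The number of treated subjects with central baseline blasts of 5% or less (k) and their chance of being scored CR/CRh* (q) are not in the documents; both are assumptions, and k may be 0.

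**1. The plan's own figures.** With exact binomials, P(X ≥ 47 of 120) is 2.00% at 30% and 91.6% at 45%, in line with the stated 90% power. For the two-look rule,

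P(success) = P(X90 ≥ 38) + Σ over x ≤ 37 of P(X90 = x) · P(Y30 ≥ 47 − x),

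which gives 2.27% at 30% and 92.0% at 45%. The design reproduces.

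**2. Is scoring ambiguous?** Take a treated subject with central baseline blasts of 5% or less. The PAS definition keeps the subject in. The central reading governs response. CR/CRh* is a state reached within two cycles, with no baseline condition, so the subject counts as a responder if the later central marrow, the absence of other disease and the blood counts all qualify. With no assessment, the subject is a non-responder. Two analysts following the text get the same answer.

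**3. How many such responders would matter?** Remove j responders from numerator and denominator and recompute the exact (Clopper-Pearson) 95% lower limit.

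| Observed | Lower limit | Last j still above 30% | First j below 30% |
|---|---|---|---|
| 47/120 | 30.4% | none removed | j = 1: 46/119, 29.9% |
| 48/120 | 31.2% | j = 2: 46/118, 30.1% | j = 3: 45/117, 29.6% |
| 50/120 | 32.7% | j = 5: 45/115, 30.2% | j = 6: 44/114, 29.6% |
| 54/120 | 35.9% | j = 11: 43/109, 30.2% | j = 12: 42/108, 29.7% |
| 38/90 (interim) | 31.9% | j = 2: 36/88, 30.5% | j = 3: 35/87, 29.9% |

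The interim bar is the 42.2% boundary rather than the 95% limit; against that bar one exclusion from 38/90 gives 37/89 = 41.6%.

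**4. Chance of success if confirmed subjects respond at only 30%.** The expected PAS rate is 0.30 + k(q − 0.30)/120. With k = 4 (three in the first 90, one in the last 30):

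| q | Expected PAS rate | P(success) |
|---|---|---|
| 0.30 | 30.0% | 2.27% |
| 0.429 (overall MT103-211 rate) | 30.4% | 2.88% |
| 0.50 | 30.7% | 3.24% |
| 0.75 | 31.5% | 4.77% |

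The value 0.75 comes from Protocol Table 6: 81/(81 + 17) = 0.827 had sufficient count recovery among those with blasts of 5% or less, times 171/189 = 0.905 assessed. It describes a post-treatment group and assumes that every later assessed marrow stays at 5% or less, so it is a high reference value and not an estimate.

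These are not type I errors. For q above 0.30 the true rate in the population being tested exceeds 30%, so the stated null hypothesis is false.

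**The case for a change.** The best case for acting is that central review is a main safeguard for an open-label, single-arm endpoint, and the plan gives it priority at baseline without using that baseline to check the primary result. A count would settle whether the question arises at all, and fixing the exclusion rule in advance prevents a choice made after the results are known. The cost is a few sentences.

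What stands is that the display is absent and would be cheap. What does not stand is that its absence leaves the plan wrong:

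- The stated hypothesis concerns treated subjects, and the PAS answers it. A centrally confirmed population is never made the target.
- Fragility at 47/120 is not specific to reader disagreement. That exact count has about 3.2% probability in 120 subjects at the 45% design rate, and there the removal of any one responder for any reason fails.
- Excluding on the central baseline is not clearly the better analysis. A low central reading may be a sampling artefact, so exclusion can drop subjects with real marrow disease.
- The documents give no sign that such subjects will be common. Protocol Section 2.5.2 places 68.8% of MT103-211 subjects at a 50% marrow blast mark on central assessment (a comparison sign seems to be lost), which suggests heavy marrow disease in a similar population, though it gives no count near 5%.

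A possible follow-up, what happens without a central baseline, is largely answered. Slides go to the central laboratory (Section 7.2.11), all marrow assessments are reviewed centrally (Section 7.2.13), Table 11 lists marrow cytomorphology as central, and a local reading exists where the central one fails.

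**Conclusion.** No change is needed. Admitting on a local reading when the central result is late is a fair trade-off in a disease where treatment may not be able to wait, and reading baseline and response centrally is the sounder choice for the endpoint. The rules combine into one unambiguous score for every subject, and the primary test keeps its exact 2.27% error for the hypothesis stated.

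The size of the effect rests on k and q, both assumed. At q = 0.429 each such subject moves the expected rate by (0.429 − 0.30)/120 = 0.11 percentage points, and four move it by 0.43 points. At the design rate the conclusion survives the exclusion of eleven such responders and fails only at the twelfth, 10% of the trial. A reader who wants reassurance can have the count, and a supportive rate without these subjects, tabulated from data the trial already collects. Neither would be decisive or bear on the success rule.
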